#### 5.3.1. Definition

- Time to pain progression is defined as the time from the date of randomization to the date of the first observation of pain progression. Pain progression is defined as an average increase by 2 points from

baseline to  $>4$  in the BPI-SF worst pain intensity (item 3) with no decrease in opioids confirmed  $\geq 3$  weeks apart or initiation of chronic opioids (see definition below), whichever occurs first. Subjects who did not experience pain progression at the time of the analysis will be censored on the last known date with no pain progression. Sensitivity analyses may be performed where increase of pain score to  $>4$  is not required, or confirmation is not required.

- Time to SRE is defined as the time from the date of randomization to the date of the first observation of an SRE. An SRE is defined as the occurrence of symptomatic pathological fracture, or spinal cord compression, or radiation to bone, or surgery to bone. Subjects who did not experience an SRE at the time of the analysis will be censored on the last known date with no SRE.
- Time to chronic opioid use is defined as the time from date of randomization to the first date of confirmed chronic opioid use. For subjects entering the study without receiving opioids, chronic opioid use is defined as administration of opioid analgesics lasting for  $\geq 3$  weeks for oral or  $\geq 7$  days for non-oral formulations. For subjects entering the study already receiving opioids, chronic opioid use is defined as a  $\geq 30\%$  increase in total daily dose of the opioid analgesics lasting for  $\geq 3$  weeks for oral or  $\geq 7$  days for non-oral formulations. Subjects with no chronic opioid use at the time of the analysis will be censored on the last known date with no chronic opioid use.
- Time to initiation of cytotoxic chemotherapy is defined as the time from the date of randomization to the date of initiation of cytotoxic chemotherapy. Subjects who did not initiate cytotoxic chemotherapy at the time of the analysis will be censored on the last known date with no cytotoxic chemotherapy.

If there is heavy censoring due to death for some secondary endpoints, sensitivity analyses counting death as event may be performed if deemed clinically meaningful.

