(PFS2) was longer for the apalutamide arm (not estimable) compared with the placebo arm (39 months). There was a 51% reduction in the risk of disease progression during first subsequent therapy or death (PFS2) for subjects originally assigned to the apalutamide + ADT arm compared with the placebo + ADT arm (HR=0.489; 95% CI: 0.361, 0.662; p<0.0001). Patient-reported outcome results indicated that there was no detriment to overall health-related quality of life with the addition of apalutamide to ADT. Similar mean changes from baseline or median time to worsening in the Functional Assessment of Cancer Therapy-Prostate (FACT-P) were observed in the 2 arms. For nearly all time points, no differences between apalutamide and placebo were observed in change from baseline across the EQ-5D index or visual analog scale.

The 3 most frequently reported TEAEs were fatigue, hypertension, and skin rash as a grouped term. Most events of skin rash were Grade 1 or Grade 2 and responded to administration of antihistamines and topical steroids; dose reduction and interruptions were also used to manage skin rash. Similarly, fatigue was mostly Grade 1 or Grade 2 which suggest that the fatigue associated with apalutamide treatment was not disabling or severe enough to interfere with activities of daily living. After adjusting for exposure, hypertension was similar in both arms and was not considered attributable to apalutamide. Fracture as a grouped term was the most commonly reported SAE, and considered serious because fracture in this elderly population often requires hospitalization. Ten percent of subjects in the study used bone-sparing agents such as bisphosphonates and denosumab. In addition to skin rash and fracture, AEs of special interest for apalutamide included fall, hypothyroidism (which was discovered since TSH was regularly monitored in Study ARN-509-003), and seizure. In Study ARN-509-003, 40% to 50% of the fractures reported in both arms were preceded by a fall (another AE of special interest) within 7 days; falls were not typically preceded by syncope or presyncope, but may have been associated with weight loss, weakness, or dizziness/vertigo. When adjusted for exposure, it appeared that apalutamide in combination with ADT did not have a clinically meaningful increase in the incidence of TEAEs compared with subjects who received ADT alone.

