Androgen deprivation therapy has been associated with increased risk of cardiovascular events, metabolic syndrome and osteoporosis. Cardiovascular and metabolic TEAEs associated with ADT use were similar between the 2 treatment arms. Fracture as a grouped term was the most commonly reported SAE in the apalutamide arm. An increased fracture risk with apalutamide may be due to an enhanced effect on the AR with apalutamide treatment.

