Overall survival is defined as the time from date of randomization to date of death from any cause.

Secondary Endpoints

- Time to pain progression is defined as the time from the date of randomization to the date of the first observation of pain progression (see also Section [9.2.1](#))
- Time to SRE is defined as the time from the date of randomization to the date of the first observation of an SRE as defined in Section [9.2.1](#)
- Time to chronic opioid use is defined as the time from date of randomization to the first date of confirmed chronic opioid use (see also Section [10.2](#))
- Time to initiation of cytotoxic chemotherapy is defined as the time from date of randomization to the date of initiation of cytotoxic chemotherapy

Other Endpoints

- Time to symptomatic local progression such as urethral obstruction or bladder outlet obstruction, is defined as the time from date of randomization to date of symptomatic local progression, whichever occurs first

- Time to PSA progression is defined as the time from the date of randomization to the date of PSA progression based on PCWG2 criteria²⁹
- Explore response markers for apalutamide, AR gene anomalies and other markers previously shown to be responsible for resistance to apalutamide
- Prostate cancer-specific survival is defined as the time from randomization to the date of death if attributed to prostate cancer
- PFS2 is defined as the time from date of randomization to date of first occurrence of disease progression on first subsequent therapy for prostate cancer or death, whichever occurs first
- Time to ECOG PS grade deterioration is defined as the time from date of randomization to the first date of deterioration in ECOG PS grade (defined as the worsening of ECOG PS grade by at least 1 point)
- Change from baseline over time in each of the subscales of FACT-P, EQ-5D-5L VAS, BPI-SF interference subscale and BFI

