10.2. Discontinuation of Study Drug

If a subject's study drug must be discontinued before disease progression this will not result in automatic withdrawal of the subject from the study. If the subject has radiographic progression

without clinical progression and alternate therapy is not initiated, treatment may continue until clinical progression is observed. All attempts should be made to capture radiographic progression even in subjects who have evidence of clinical progression.

However, a subject's study treatment must be discontinued for:

- Clinical progression defined as:
 - Deterioration in ECOG PS grade to grade 3 or higher (related to prostate cancer progression)
 - Need to initiate any of the following because of tumor progression (even in the absence of radiographic evidence of disease)
 - Subsequent anti-cancer therapy for metastatic prostate cancer
 - Radiation therapy for metastatic prostate cancer lesion(s) (palliative radiation to lesions existing at baseline will not be considered clinical progression)
 - Surgical interventions for complications due to metastatic prostate cancer progression. (Note: Surgical interventions for complications of local-regional progression are not considered clinical progression)
 - Need for chronic opioid analgesics: For subjects entering the study without receiving opioids, chronic opioid use is defined as administration of opioid analgesics lasting for ≥ 3 weeks for oral or ≥ 7 days for non-oral formulations. For subjects entering the study already receiving opioids, chronic opioid use is defined as a $\geq 30\%$ increase in total daily dose of the opioid analgesics lasting for ≥ 3 weeks for oral or ≥ 7 days for non-oral formulations. NOTE: Administration of as needed (eg, not fixed or scheduled dosage) use of opioid analgesics or extended opioid use for treatment other than the subject's prostate cancer does not require discontinuation from study treatment (eg, codeine/acetaminophen combinations, hydrocodone/acetaminophen combinations, hydrocodone/ibuprofen combinations, oxycodone/acetaminophen combinations, oxycodone/aspirin combinations, tramadol)
- More than 2 dose level reductions for Grade 3 or higher treatment-related AEs (see [Table 1](#) and [Table 2](#))
- Seizure of any grade or Grade 4 neurotoxicity
- Subjects who have had their treatment assignment unblinded for any reason except for IDMC recommendation to unblind the study

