#### **1.1.2. Secondary Objectives**

- To evaluate clinically relevant improvements with addition of apalutamide to ADT including delays in pain progression and opioid use for prostate cancer, skeletal-related events, and the need for cytotoxic chemotherapy
- To characterize the safety of adding apalutamide to ADT in subjects with mHSPC
- To characterize the population pharmacokinetics (PK) and pharmacodynamics (PD) of apalutamide
- To evaluate the concentration of leuprolide and assess the PD effect of leuprolide on testosterone concentrations when used alone or in combination with apalutamide
- To evaluate the treatment effectiveness with the addition of apalutamide to ADT for the subpopulations of subjects with low-volume or high-volume mHSPC

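### The SAP's chronic opioid event has no indication limit, although the secondary objective is opioid use for prostate cancer

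*SAP*

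**What the plan says.** The secondary objectives (Protocol 2.1, SAP 1.1.2) include "delays in pain progression and opioid use for prostate cancer".

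SAP 5.3.1 gives the event rule. For men not on opioids at entry: "For subjects entering the study without receiving opioids, chronic opioid use is defined as administration of opioid analgesics lasting for" at least 3 weeks (oral) or at least 7 days (non-oral). For men already on opioids it is a rise of at least 30%, worded as an "increase in total daily dose of the opioid analgesics lasting for" the same periods. Neither sentence names an indication or says how as-needed use is treated. SAP 5.3.1 also makes initiation of chronic opioids, under this definition, one way to reach pain progression.

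Protocol 9.2.3 says: "Time to chronic opioid use is defined as the time from date of randomization to the first date of confirmed chronic opioid use", and refers to Section 10.2. Protocol 9.2.1 refers to the same section for the opioid part of pain progression. In Section 10.2, chronic opioid need is listed under clinical progression, in a list that contains the lead-in "Need to initiate any of the following because of tumor progression". A NOTE there adds that as-needed use or "extended opioid use for treatment other than the subject's prostate cancer does not require discontinuation from study treatment".

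**The concern.** The objective is limited by indication and the SAP event is not. Read literally, the rule makes any opioid course that meets the duration or dose condition an event, including one given for a reason unrelated to prostate cancer. Such courses carry no information about delay of cancer-related opioid use. They move the hazard ratio towards whatever ratio holds for non-cancer courses, which is 1 if the drug does not affect them.

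Two of the four secondary endpoints share the definition. The risk is an understated effect on the stated objective and an endpoint that is hard to interpret. There is also a practical problem: two programmers, one working from the SAP sentence and one from Section 10.2 as a whole, could code the endpoint differently.

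**Working it through.** No figure in the plan depends on this rule, so there is none to reproduce. The check compares the texts and then illustrates the size.

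**Step 1. What each text covers**

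| Text | Limited to prostate cancer? | As-needed use addressed? |
|---|---|---|
| Objective (Protocol 2.1, SAP 1.1.2) | Yes | No |
| Protocol 9.2.3, endpoint | Not itself; refers to 10.2 | Not itself; refers to 10.2 |
| Protocol 10.2, defining sentences | No | No |
| Protocol 10.2, context and NOTE | Listed under clinical progression; other use set apart, for discontinuation only | Yes, for discontinuation only |
| SAP 5.3.1, event | No | No |

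The SAP repeats the defining sentences of 10.2 without the context or the NOTE.

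**Step 2. Follow one case through the rules.** A man without opioids at entry takes oral opioids for more than 3 weeks for a condition other than prostate cancer.

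- Objective: this is not the outcome of interest.
- Protocol 10.2: the NOTE applies, and the course does not require him to stop study drug.
- SAP 5.3.1: he has an event for time to chronic opioid use and also for time to pain progression.

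**Step 3. Look for a provision that catches this.** The optional sensitivity analyses in SAP 5.3.1 vary the pain-score threshold, the confirmation requirement and the handling of death. None varies the indication. By contrast, the fracture component of the skeletal-related event is limited to symptomatic pathological fracture, so the plan does draw a disease-related line for a neighbouring endpoint.

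**Step 4. Are the data there?** Protocol Section 8 records the indication of concomitant drugs from consent to 30 days after the last dose. For the Follow-up Phase, the Time and Events Schedule lists opioid use and does not mention indication.

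**Step 5. Illustration of size; every input is assumed.** Let HRc be the hazard ratio for cancer-related chronic opioid use, s the non-cancer share of the control-arm hazard, and g the apalutamide-to-placebo ratio for non-cancer courses. If the two hazards add, then

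observed HR = (1 − s) × HRc + s × g.

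With HRc = 0.75 and g = 1 (equal rates in both arms):

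- s = 5%: 0.95 × 0.75 + 0.05 × 1 = 0.7625, about 0.76
- s = 10%: 0.90 × 0.75 + 0.10 × 1 = 0.775, about 0.78
- s = 20%: 0.80 × 0.75 + 0.20 × 1 = 0.80

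If non-cancer courses were more frequent on apalutamide, the same shares would give 0.79, 0.83 and 0.90 (g = 1.5) or 0.81, 0.88 and 1.00 (g = 2). The formula is a weighted average, so the shift is towards 1 or beyond whenever g is at least 1. There would be no shift if g equalled HRc. The documents give none of HRc, s or g.

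**The case against.** The best defence is that the documents should be read together. The SAP describes itself as a supplement to the protocol. Protocol 9.2.3 sends the reader to Section 10.2, where chronic opioid need sits within clinical progression and non-cancer use is set apart. On that reading the limit is already there. The exact list level of the opioid item is unclear in the available text, so the tumor-progression lead-in may or may not govern it.

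An all-indication rule also has merits. It is objective and needs no attribution. Attribution could be influenced by PSA results, which investigators see from Cycle 5. The endpoint is secondary, and its significance can be claimed only if both rPFS and OS are significant. In pain progression the worst-pain score is not attributed to cancer either, so limiting only the opioid part leaves a mixed composite.

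Most of this stands and keeps the point small. It does not close the gap, because no passage says that non-cancer use is excluded from either endpoint and the SAP sentence, which will be programmed, includes it. The attribution worry is a reason for blinded review and a parallel all-indication analysis.

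A reader might infer more: that the protocol excludes non-cancer opioids from the endpoint and the SAP contradicts it. The documents do not support that. The defining sentences in 10.2 name no indication, and the NOTE concerns only whether study drug must stop. It shows that the distinction was recognised; it does not define the endpoint.

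**Conclusion.** The point holds as a mismatch between objective and event definition, and correcting it is a cheap improvement. As written, non-cancer opioid courses count in two secondary endpoints and dilute the comparison on the stated objective, provided their ratio between arms is nearer to 1 than the cancer-related hazard ratio. The size cannot be computed from the documents; the worked figures show only how the dilution behaves under assumed inputs.

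A reader might also infer that fracture pain would count against apalutamide, since the protocol says in Section 1.1.2.1: "An increased fracture risk with apalutamide may be due to an enhanced effect on the AR with apalutamide treatment". A difference between arms by this route is possible but not shown:

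- The statement concerns an earlier study in non-metastatic castration-resistant disease, and no fracture rate by arm is given.
- The same section says that "40% to 50% of the fractures reported in both arms were preceded by a fall", which applies to both arms.
- Every man in this trial must have a bone metastasis, so some fractures will be pathological, and opioids for those are prostate-cancer use.
- Nothing shows that fractures lead to opioid courses long enough to meet the rule.

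The cases with g above 1 are therefore hypothetical. If there were such a difference, it would work against apalutamide, so this is not a route to a false claim in the drug's favour.

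**What to change.** In SAP 5.3.1:

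- Limit the chronic opioid event to opioid use for prostate cancer, in both time to chronic opioid use and the opioid part of time to pain progression. Decide this from the recorded indication, reviewed blind to treatment arm.
- Count courses with unknown indication as events, including those in follow-up where indication may not be collected.
- Keep the present all-indication definition as a sensitivity analysis for both endpoints.
- State how the Section 10.2 NOTE on as-needed use applies to the endpoint.

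The treatment discontinuation rule stays as it is.

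The cost is a few sentences in the SAP and a blinded review of recorded indications. The downsides are some attribution judgement and incomplete indication data beyond 30 days after the last dose. Counting unknowns as events leaves some dilution in place, but it does not drop events because a field is missing. Setting the result beside the all-indication analysis shows how much the classification matters.

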### 5.3.2. Censoring Rules

For all these time-to-events endpoints, subjects with no on-study assessment or no baseline assessment will be censored on the date of randomization (see Sections 5.2.1.2 and 5.3.1).

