9.1.5. Follow-up Phase

The Follow-up Phase should begin once a subject discontinues study drug for any reason. During the Follow-up Phase information will be collected every 4 months until death, withdrawal of consent, lost to follow-up or termination of the study. The information collected during follow-up will include the following: survival, data on secondary endpoints (see Section 9.2.3), first subsequent therapy for prostate cancer, date and type of disease progression (radiographic, PSA, clinical or a combination) on the first subsequent systemic therapy for prostate cancer, and PROs (see Time and Events Schedule). Some follow-up information may be performed by telephone interview or chart review or other convenient methods, and will be reported on the eCRF.

During the Follow-up Phase, deaths regardless of causality and treatment-related SAEs will be collected and reported within 24 hours of discovery or notification of the event on the eCRF.

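### SAP 5.3.2 censors at randomization any subject with no baseline or no on-study assessment, which conflicts with SAP 5.3.1 for skeletal-related events and cytotoxic chemotherapy, endpoints that need no such assessment

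*SAP*

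**What the plan says.** SAP 5.3.2 consists of one sentence: "For all these time-to-events endpoints, subjects with no on-study assessment or no baseline assessment will be censored on the date of randomization". It then refers the reader to 5.2.1.2 and 5.3.1. The endpoints covered are time to pain progression, SRE, chronic opioid use and cytotoxic chemotherapy.

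SAP 5.3.1 treats each endpoint separately.

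- **SRE:** "An SRE is defined as the occurrence of symptomatic pathological fracture, or spinal cord compression, or radiation to bone, or surgery to bone". For censoring, "Subjects who did not experience an SRE at the time of the analysis will be censored on the last known date with no SRE".
- **Chemotherapy:** "Time to initiation of cytotoxic chemotherapy is defined as the time from the date of randomization to the date of initiation of cytotoxic chemotherapy", with parallel censoring wording.
- **Chronic opioid use:** the definition divides by opioid status at entry. Non-users need a sustained course. Users at entry need a sustained rise of at least 30% in total daily dose.
- **Pain progression:** either a confirmed worsening of the BPI-SF worst-pain item from baseline, "or initiation of chronic opioids (see definition below), whichever occurs first".

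The protocol's Time and Events Schedule collects SREs, opioid use and chemotherapy every 4 months in follow-up. On method, Protocol 9.1.5 says: "Some follow-up information may be performed by telephone interview or chart review or other convenient methods". SAP Section 5 places all efficacy analyses in the ITT population.

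**The concern.** SRE and chemotherapy are dated clinical events. Neither is a change from a baseline score, and neither needs a scheduled questionnaire or scan in order to be dated. A rule triggered by a missing assessment therefore has no natural link to them.

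A subject censored on day 0 enters no risk set after randomization. He remains in the ITT population by name but contributes nothing to the log-rank test or the Cox model. Under SAP 5.3 these endpoints can carry claims of significance once rPFS and OS are both significant, so their event counts should not depend on which of two sections a programmer follows. SAP 5.1.2 plans no imputation and makes sensitivity analyses of censoring rules optional.

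**Working it through.** The plan gives no event count, power or missing rate for any secondary endpoint, so it has no figure of its own to reproduce here. The check is first textual, then a range under stated assumptions.

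**Step 1: the two sections side by side.** Take two men with no baseline assessment.

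- One starts chemotherapy in month 8. Under 5.3.1 he is an event at month 8. Under 5.3.2, read literally, he is censored at time 0.
- The other is known to be free of chemotherapy at month 24. Under 5.3.1 he is censored at month 24. Under 5.3.2 he is censored at time 0.

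The cross-references do not settle which section governs. SAP 5.2.1.2 (Table 2) ties its day-0 rule to tumor assessments, which suits rPFS but has no bearing on when chemotherapy began. SAP Table 3 uses nearly the same sentence for ECOG deterioration, where a baseline grade is needed.

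**Step 2: what each endpoint needs.**

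- SRE and chemotherapy need no baseline assessment.
- The BPI-SF route to pain progression needs a baseline score.
- Chronic opioid use, alone or as the second route to pain progression, needs entry opioid status and, for users at entry, the entry dose. Protocol Section 8 has medications recorded in the eCRF from consent, so this information does not depend on a scheduled assessment.

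**Step 3: events affected.** Events affected = N × missing share × event probability, with N = 1,000 from the plan and the other two inputs assumed. For example, 1,000 × 0.05 × 0.20 = 10.

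**Step 4: power.** Power = Φ(√(D/4) × |ln HR| − 1.96), assuming HR 0.67, two-sided 0.05 and D = 200 events before any loss. D is then reduced by the missing share. At D = 200: √50 × 0.4005 − 1.96 = 0.872, so power is 0.808.

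| Missing share | Subjects | Events affected at 10 / 20 / 30% | D left of 200 | Power |
|---|---|---|---|---|
| 1% | 10 | 1 / 2 / 3 | 198 | 0.804 |
| 2% | 20 | 2 / 4 / 6 | 196 | 0.800 |
| 5% | 50 | 5 / 10 / 15 | 190 | 0.788 |
| 10% | 100 | 10 / 20 / 30 | 180 | 0.766 |

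**Step 5: bias.** A simulation used 500 subjects per arm, exponential event times, 24 months of follow-up, a 20% control event probability, a true HR of 0.67 and 2,000 replicates. It compared the ratio of event rates in all randomized subjects with the ratio after removing those who lack an assessment.

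| Missing, placebo / apalutamide | Hazard in the missing | All randomized | After the rule |
|---|---|---|---|
| 5% / 5% | same | 0.666 | 0.666 |
| 5% / 5% | doubled | 0.669 | 0.668 |
| 2% / 5% | doubled | 0.688 | 0.669 |
| 5% / 2% | doubled | 0.652 | 0.668 |

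The ratio moves noticeably only in the last two rows, by 0.019 and 0.016, in opposite directions.

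**The case against.** The strongest reply is that 5.3.2 should be read together with 5.3.1: a recorded event counts first, and the day-0 rule only sets the time for event-free men with no assessment. The cross-reference to 5.3.1 makes this possible, and the SAP does not define an assessment for SRE, opioid use or chemotherapy. A reader might infer that recorded events will certainly be discarded; the documents do not support that certainty. But the reconciling reading is not written down, and it does not remove the conflict. Event-free men would still get time zero where 5.3.1 follows them to their last event-free date. Among men with no assessment, only those who go on to have the event would then contribute time at risk, which is not a sound risk set.

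Second, few men may be affected. Protocol 4.1 and 4.2 require a bone scan and screening laboratory values, Section 4 allows no waivers, and 9.1.4 schedules an End-of-Treatment visit for most who stop. A man whose event was found in follow-up has arguably been assessed on study for that endpoint. This stands as an argument about size. It does not settle the wording, because SAP 6.1 uses on-study for the period up to 30 days after the last dose, as opposed to follow-up.

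Third, a reader might group chronic opioid use with the endpoints that need no baseline information. The definition in 5.3.1 does not allow this: entry status, and entry dose for users, must be known.

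Fourth, a reader might infer that the loss is related to outcome and biases the comparison. The documents give no evidence of this. A missing baseline arises at or before the first dose of a double-blind trial, so there is little reason to expect imbalance by arm from that source.

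**Conclusion.** The concern holds as an internal conflict with a cheap remedy. Sections 5.3.1 and 5.3.2 prescribe different results for a man who lacks an assessment, whether or not he has had an SRE or started chemotherapy. On the literal reading, recorded events and event-free follow-up leave an ITT analysis for a reason unrelated to the endpoint.

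The size cannot be derived from the documents. About 1-30 events per endpoint is the range under the assumed missing shares and event probabilities, and the effect is probably small. At 5% missing, illustrative power falls from 0.808 to 0.788. Bias would need missingness that is both related to outcome and unbalanced by arm; with both imposed, the hazard ratio moved by about 0.02, in either direction. The rule does not touch rPFS or OS, so the primary conclusion is unaffected. The point does not extend unchanged to chronic opioid use, which needs its own rule for entry information.

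**What to change.** Replace the sentence in SAP 5.3.2 with a rule for each endpoint:

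- **Day-0 censoring:** keep it only for the BPI-SF component of pain progression when the BPI-SF baseline or all later BPI-SF scores are missing, and for subjects with no post-randomization information at all on the endpoint.
- **SRE and chemotherapy:** count any recorded event on its date; otherwise censor at the last known event-free date, as 5.3.1 already provides.
- **Chronic opioid use, and the opioid component of pain progression:** do the same, taking entry opioid status and dose from the concomitant-medication record, and state how unknown entry status or dose is handled. A man without a BPI-SF baseline then stays at risk through the opioid route.

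The cost is a few sentences in the SAP and matching derivation rules. No new data are needed, since the protocol already collects these events in follow-up. The change should be made before the analysts have access to treatment codes. The report should give, by arm, the number of subjects censored on day 0 for each endpoint.
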